Project Title

End Tidal CO2 and Masks: Is There a Correlation?

Co-Investigator Information

[name] MD
Department of Emergency Medicine
CHRISTUS Spohn Hospital Corpus Christi-Shoreline
[contact]/[contact]
[contact]

[name] MD
Department of Emergency Medicine
CHRISTUS Spohn Hospital Corpus Christi-Shoreline
[contact]
[contact]

[name]
Department of Emergency Medicine
CHRISTUS Spohn Hospital Corpus Christi-Shoreline
[contact]
[contact]

[name]
Shoreline Research Coordinator
CHRISTUS Spohn Hospital Corpus Christi-Shoreline
[contact]
[contact]

Principal Investigator

[name], DO
Emergency Medicine Resident
CHRISTUS Spohn Hospital Corpus Christi-Shoreline/Memorial
[contact]
[contact]

Objectives

The primary objective of this study is to evaluate if there are changes present with end tidal carbon dioxide while wearing a mask. A secondary objective is to assess possible changes in end tidal carbon dioxide while walking moderate distances while wearing a mask.

Research Question/Hypothesis

This aim of this study is to test the null hypothesis that end tidal carbon dioxide (ETCO2) will not change with mask wearing while at rest and while walking a moderate distance of 100 meters in a small sample of healthy adult volunteers.

Background to Research Questions

In light of the ongoing COVID-19 pandemic, wearing a mask has become a universal standard as an attempt to reduce the spread of COVID-19. As of 2020, more than half of all U.S. states have implemented a state wide mandated mask policy¹. There are many schools of thought regarding the benefits and risks of donning a mask to prevent the spread of COVID-19. There is an unproven theory among some that wearing a mask interferes with our natural respiratory function, causing hypoxia, altered mental status and other various health issues⁴. This dangerous perception has led some to believe wearing a mask is harmful, and encourages against wearing a mask in public. This theory, recently refuted by a study investigating oxygen levels while participants wore masks, performed in 2020 by Chan et al. encouraged increased compliance with wearing masks². Another study, preformed by Samannan et al, evaluated whether gas exchange abnormalities occurred with the use of surgical masks in subjects with and without lung function impairment⁶. The conclusions of the Samannan studied showed that regardless of lung function impairment, the presence of surgical masks did not impact gas exchange⁶.

Additionally, a more recent study conducted by Barbeito-Caamano et al concluded that the presence of a facemask did not have a significant change in physiologic parameters while during exercise⁵. Although there is evidentiary support that facemasks do not negatively affect oxygen status² and physiologic capacity, there is not strong evidence examining the relationship between ETCO2 and facemasks. The relationship between ETCO2 and facemasks is one of importance because mild decreases in oxygen have much less dangerous effects compared to the effects of rapid accumulations of carbon dioxide. Increases in end tidal carbon dioxide lead to confusion, acidosis and in severe cases, respiratory distress and failure. A study performed by Somers et al., in 1989 showed that hypercapnia has greater increases in blood pressure, minute ventilation and sympathetic nerve activity than hypoxia³.

In this newly proposed study, healthy volunteers will all wear the same type of three layer surgical mask. Their end tidal carbon dioxide will be measured while at rest without a mask, while resting with a mask and then after walking 100 meters in the mask. While previous studies have focused on changes in oxygen, there is a lack of research dedicated to analyzing end tidal carbon dioxide. This study will hope to show evidence supporting that there is no increase in end tidal carbon dioxide while wearing a mask.

METHODOLOGY

Study design

This study is a prospective, controlled study involving healthy adult volunteers all of whom are resident and faculty physicians, or other medical staff. There will be no financial compensation.

Intervention

After obtaining appropriate consent, subjects will have their end tidal carbon dioxide levels measured in three separate scenarios. Subjects will have their baseline end tidal carbon dioxide measured while at rest and without a mask. The second measurement will also occur at rest, but while subjects are wearing a mask. Lastly, end tidal carbon dioxide will be measured after each participant walks 100 meters, both with and without a surgical mask. These values will be compared during the data collection. In each of these scenarios, volunteers will also have their oxygen saturation measured.

Setting

A maximum of 200 healthy adults will be enrolled at a Level 2 trauma center. Activities will be conducted inside of the hospital, where there is a large enough space to accommodate subjects walking the length of 100 meters. They will walk 100 meters twice, for a total of 200 meters.

Expected Start Date

Upon IRB approval.

Duration of Study

The study should take approximately six months to gather the data. An additional six months will be required to analyze the data and to prepare the study findings.

Study Subjects

The sample population will include Residents and staff members at Christus Spohn Shoreline. The maximum number of participants for this study will be 200.

Inclusion Criteria:

Healthy individuals between the ages of 18 and 75

Consent to participate in this study

Resident and ancillary staff

Exclusion Criteria:

Patients

Inability or refusal consent

Inability to walk the predetermined distance

History of lung disease

History of significant cardiac disease
People under the age of 18 and over the age of 75

Equipment/Supplies/Services

Supplies and services used for the study will consist of standard issued surgical masks, portable vital sign monitors of an undetermined brand, end tidal carbon dioxide measuring device better known as mask capnography, oxygen saturation measurement device, respiratory therapists.

Data Collection

Trained respiratory therapists will use the portable monitors to measure End tidal carbon dioxide values as well as oxygen saturation values. All values will be recorded into Excel.

Data Analysis

Statistical support will be provided by a member of the research team specializing in statistical analysis. De-identified ordinal data will be entered into an Excel spreadsheet and imported into a statistical analysis software program. Data will be analyzed by chi-square testing.

Data Management

There will be minimal collection of protected health information including a name and signature. All data will be de-identified. Numerical data will be stored on a private, secure computer, owned by the principal investigator under fingerprint and password encryption. The signed consent forms will be kept in a locked file, stored in the locked office of [name], Research Coordinator. Her office is located on the 9th floor administrative office of CHRISTUS Spohn Hospital Corpus Christi-Shoreline. Only the Principal Investigator, Co-Investigators, and Statistician will have access to the data. All identifying information will be destroyed upon completion of the study.

Identified Risks/Ethical Considerations

Foreseeable risks include participant discomfort, shortness of breath and incidental exposure to COVID-19 as there will be measurements taken while a mask is not worn. There will be a session of counseling to discuss risks and complications of the participating in the study. There is a possible risk of breach of confidentiality. However, all effort will be made to protect the subjects' personal information. Identifying features of the patients will not be used, recorded, or presented in any abstract, manuscript, or oral presentation.

Benefits of Proposed Research to the Subjects and Others

Results of this study should disprove the theory that wearing a face mask interferes with natural respiratory function, causing hypoxia, altered mental status and other various health issues and instead provide evidence of the safety in compliance of wearing face masks in public to reduce exposure to the COVID-19 virus. This will benefit the general public by encouraging ongoing compliance with mask wearing policies.

Study Registration

This study will be registered with Clinicaltrials.gov after approval by the IRB and prior to participant enrollment.

References

1. <https://masks4all.co/what-states-require-masks/>

3. Somers, V. K., et al. "Contrasting Effects of Hypoxia and Hypercapnia on Ventilation and Sympathetic Activity in Humans." *Journal of Applied Physiology*, vol. 67, no. 5, 1989, pp. 2101–2106., doi:10.1152/jappl.1989.67.5.2101.

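### A chi-square test of a no-change null cannot support the intended conclusions of no increase, disproof and safety, some of which concern outcomes that are not measured

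*Protocol*

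**What the plan says.** All references are to the Protocol.

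- **Objectives.** The primary objective is neutral: to "evaluate if there are changes present with end tidal carbon dioxide while wearing a mask".
- **Research Question/Hypothesis.** The aim is to "test the null hypothesis that end tidal carbon dioxide (ETCO2) will not change with mask wearing while at rest" and also over a 100 m walk.
- **Background to Research Questions, last paragraph.** The hoped-for result has a direction: "This study will hope to show evidence supporting that there is no increase in end tidal carbon dioxide while wearing a mask".
- **Intervention.** Each person is measured at rest and after walking, with and without a mask. "In each of these scenarios, volunteers will also have their oxygen saturation measured". No other outcome is listed.
- **Study Subjects.** "The maximum number of participants for this study will be 200". No minimum or target is given. Participants are healthy residents and staff; the exclusions include "History of lung disease" and significant cardiac disease.
- **Data Analysis.** "Data will be analyzed by chi-square testing". No other method is named, and the data are described as ordinal.
- **Benefits of Proposed Research.** "Results of this study should disprove the theory that wearing a face mask interferes with natural respiratory function". The sentence goes on to name hypoxia, altered mental status and unspecified other health problems, and ends with evidence that wearing masks in public is safe.

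**The concern.** The conclusion that the investigators hope for is essentially the null hypothesis of their own test. A test of no difference can reject its null but cannot establish it. For a statement that masks do not raise end tidal CO2, the error that matters is saying so when a rise exists. The significance level of a no-change test does not control that error.

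The named test makes this harder to repair. End tidal CO2 is a numerical reading taken on the same person under each condition. A chi-square test needs categories, and none is defined. In its ordinary form it treats the masked and unmasked readings as independent groups. It also yields no upper bound on the mean rise, which is what a no-increase statement needs.

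A second limb needs no arithmetic. The Benefits section draws conclusions about outcomes that the study does not record, and about the public at large from healthy hospital staff. The Background itself treats raised CO2 as the more dangerous disturbance, and the result is meant to encourage compliance with mask policies, so an unsupported reassurance would matter.

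**Working it through.** **Step 1. Possible results against the intended conclusion.** The null is no change in end tidal CO2.

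- Significant rise: contradicts the hoped-for conclusion.
- Significant fall: would support no increase, but is not what the Protocol anticipates.
- Non-significant: the only remaining result that could be offered for no increase. It is compatible with a true rise that the study was too imprecise to detect.

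**Step 2. Inputs.** The Protocol gives no significance level, SD, effect size, margin or cut point. Its only sample figure is the cap of 200, so there is no stated figure to reproduce. Everything below is illustration. The assumptions are a two-sided 0.05 level, an SD of within-person differences (SDd) of 3 to 5 mmHg, true rises (d) of 1 and 2 mmHg, and sample sizes of 50 and 100 as well as the cap.

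**Step 3. Paired t-test.** The probability of non-rejection comes from the noncentral t distribution with n − 1 df and noncentrality d·√n/SDd. For example, with n=200, d=1 and SDd=5, the noncentrality is √200/5 = 2.83, the critical value is 1.97, and non-rejection is 0.196.

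| n | d=1: SDd 3 / 4 / 5 | d=2: SDd 3 / 4 / 5 |
|---|---|---|
| 50 | 0.363 / 0.590 / 0.716 | 0.004 / 0.066 / 0.208 |
| 100 | 0.090 / 0.303 / 0.492 | 0.000 / 0.001 / 0.023 |
| 200 | 0.003 / 0.060 / 0.196 | about 0 throughout |

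**Step 4. Chi-square, in one assumed layout.** With no categories stated, the error rate of the planned test cannot be fixed. As an illustration, split end tidal CO2 at the no-mask median, take a between-person SD of 4 or 5 mmHg, bivariate normal readings with correlation 1 − SDd²/(2·SD²), n=200, no continuity correction, and 20,000 simulated trials per setting. A 1 mmHg rise then moves the share above the cut from 50% to Φ(1/4) = 60% or Φ(1/5) = 58%.

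- Ordinary 2×2 chi-square, pairing ignored: a 1 mmHg rise is missed about 49% to 72% of the time; a 2 mmHg rise at most about 8%.
- McNemar (paired) chi-square on the same split: a 1 mmHg rise is missed about 20% to 50% of the time; a 2 mmHg rise about 3% or less.
- Paired t-test at the same n, from step 3: 0.3% to 20%, and about 0%.

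**Step 5. What an interval would give.** The 95% CI half-width is t(0.975, n − 1)·SDd/√n. For SDd of 3 to 5 mmHg it is 0.85 to 1.42 mmHg at n=50, 0.60 to 0.99 at n=100 and 0.42 to 0.70 at n=200. An interval therefore says directly how large a rise the data exclude.

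**Step 6. Scope.** Recorded: end tidal CO2 and oxygen saturation, at rest and after 100 m. Concluded on in the Benefits section: respiratory function, hypoxia, mental status, other health problems and safety in public. Saturation bears on hypoxia. Mental status and the other health problems have no measurement behind them, and the population excludes lung and significant cardiac disease.

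**The case against.** The strongest reply is that the Protocol never says a non-significant result will be read as no increase. The primary objective is neutral, no decision rule is stated, and the optimistic sentences stand in Background and Benefits. A statistical analysis plan, not shown here, could hold intervals, interpretation rules or a margin. This stands in part. A reader might infer that the investigators have committed themselves to declaring safety from a non-significant p-value; the document does not support that. What it does support is narrower: a no-change null and a single named test, set beside conclusions that the test cannot deliver.

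A second reply is that the size of the problem depends on the rise chosen. This stands. Near the cap a 2 mmHg rise would hardly ever be missed by a paired t-test, and at most about 8% of the time in the assumed chi-square layouts. Part of the 49% to 72% figure comes from ignoring pairing, which the Protocol does not actually specify. A reader might infer that the study is too small to detect a rise of any importance; the figures do not show that.

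A third reply is that the Background links raised CO2 to confusion, so end tidal CO2 stands in for mental status. That link is a rationale for choosing the outcome. It is not a measurement of mental status, and it does not cover the other health problems or safety in public.

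**Conclusion.** The point holds. As written, the hypothesis and the named test cannot support no increase, disproof of harm or safety. Barring a significant fall, non-rejection is all that could be offered, and the reading that it would be so offered is an inference from the Background and Benefits wording. Chi-square is also a poor choice in itself for paired numerical readings. The overreach to unmeasured outcomes and to the public rests on the text alone.

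The practical size cannot be fixed from the document. On the assumed SDs it is substantial for a 1 mmHg rise if few people enrol, and modest near the cap under a paired analysis. At the cap it is larger for a 1 mmHg rise under a median-split chi-square, and small for a 2 mmHg rise under any of these analyses. This should be corrected, with moderate confidence. It does not undermine the measurements, which would still allow a sound analysis.

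**What to change.** Before enrolment:

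1. In Data Analysis, replace chi-square with the mean paired mask-minus-no-mask difference in end tidal CO2 and its 95% CI: rest as primary, walk with mask minus walk without as secondary.
2. State that a non-significant result will not be read as absence of an increase.
3. In the Background and Benefits sections, limit the conclusions to what the end tidal CO2 and saturation intervals exclude in healthy volunteers.
4. Drop direct claims on mental status, other health problems and general safety in public. The link from CO2 to confusion may stay as rationale.
5. Only if a claim of no important increase is wanted, pre-specify and justify a margin, and make the claim only if the upper 95% limit lies below it. This does not replace item 4.

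The cost is one change of analysis on values already to be recorded, plus rewording; no extra measurement is needed. If a margin is used, the cap is probably adequate. With a true rise of 0, n=200 and SDd of 3, 4 or 5 mmHg, a 1 mmHg margin (an example, not a proposal) would have power of 0.997, 0.940 or 0.804. The downside for the investigators is that a non-significant result no longer supports the hoped-for claim by itself.

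### At rest every volunteer is read unmasked first and masked second, so the resting mask effect cannot be separated from a period effect

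*Protocol*

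**What the plan says.** The Objectives section of the Protocol states: "The primary objective of this study is to evaluate if there are changes present with end tidal carbon dioxide while wearing a mask". Walking is a separate, secondary objective. The null hypothesis is that "end tidal carbon dioxide (ETCO2) will not change with mask wearing while at rest and while walking a moderate distance of 100 meters".

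The Intervention section sets the order of the resting readings. The first is unmasked: "Subjects will have their baseline end tidal carbon dioxide measured while at rest and without a mask". The next is masked: "The second measurement will also occur at rest, but while subjects are wearing a mask". The Background section gives the same sequence, with ETCO2 "measured while at rest without a mask, while resting with a mask and then after walking 100 meters in the mask".

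For the walks, the Intervention section says: "Lastly, end tidal carbon dioxide will be measured after each participant walks 100 meters, both with and without a surgical mask". It does not say which walk comes first.

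On analysis, the Data Analysis section says: "Data will be analyzed by chi-square testing". On size, Study Subjects says: "The maximum number of participants for this study will be 200". The Protocol does not mention a randomised or alternating order, a second unmasked resting reading after the masked one, a group measured twice without a mask, or an interval before each reading.

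**The concern.** Using each volunteer as their own control removes differences between people. It does not remove differences between the first and the second reading. Resting ETCO2 may move between two readings because the person settles, gets used to the capnograph, or because the monitor drifts. With one order for everyone, any such movement is counted in full as mask effect.

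The error can go either way. An upward shift could create a false rise. A downward shift could hide a real one, which matters here because the Background section hopes to show no increase and the Benefits section expects the results to support continued mask wearing. Enrolling more volunteers leaves the bias unchanged and makes a spurious difference more likely to reach significance.

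**Working it through.** The Protocol states no power, alpha, effect size or SD, so there is no figure of its own to reproduce. The check has two parts. The first needs no assumed numbers.

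**1. Can mask and period be separated at rest?** Let τ be the mask effect, π the shift from first to second reading, and D the masked minus the unmasked value in one person.

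- Fixed order (unmasked, then masked): E(D) = τ + π for everyone. With columns for intercept, mask and period, the two readings are (1,0,0) and (1,1,1). The mask and period columns are identical, so the rank is 2 with 3 parameters. τ cannot be estimated separately from π.
- Balanced order: E(D) = τ + π when unmasked comes first and τ − π when masked comes first. The average of the two group means is τ. The rank is 3 of 3.
- Carryover: if wearing the mask first shifts the later unmasked reading by c, the masked-first mean becomes τ − π − c. The average is then τ − c/2, a bias of c/2 in size.

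**2. How much could it matter?** This part is illustrative. The following are assumptions, not in the Protocol: a paired t-test (the Protocol names chi-square), two-sided alpha 0.05, SD of paired differences 2, 3 or 4 mmHg, drift 0.25 or 0.5 mmHg, and n = 50. The value n = 200 is the Protocol's maximum.

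With τ = 0 the t statistic is noncentral t with n − 1 degrees of freedom and noncentrality λ = drift × √n / SD. For drift 0.5, SD 2 and n = 200, λ = 0.5 × 14.14 / 2 = 3.54, the critical value is 1.97, and P(reject) = 0.940.

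Probability of p<0.05 with no mask effect, fixed order:

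| Drift (mmHg) | n | SD 2 | SD 3 | SD 4 |
|---|---|---|---|---|
| 0.25 | 50 | 0.139 | 0.089 | 0.072 |
| 0.25 | 200 | 0.421 | 0.216 | 0.142 |
| 0.5 | 50 | 0.410 | 0.211 | 0.139 |
| 0.5 | 200 | 0.940 | 0.650 | 0.421 |

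Simulating a balanced order with period adjustment (20,000 runs per setting), with 0.5 mmHg common drift and no mask effect, gave a mean estimate of 0.00 and rejection of 4.9% to 5.1% in all six combinations of SD and n. Adding a 0.5 mmHg differential carryover gave a mean bias of 0.25 mmHg, which is c/2.

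For the opposite error, take τ = +0.5 and drift −0.5 mmHg. Under the fixed order E(D) = 0, so the rise is detected in 5% of studies at any n. The balanced order gave a mean estimate of 0.50 and detected the rise in 0.404, 0.213 and 0.137 of runs at n = 50, and in 0.940, 0.652 and 0.421 at n = 200 (SD 2, 3, 4).

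**The case against.** **The resting pair is not named as the primary contrast.** The primary objective does not say at rest, and the hypothesis covers rest and walking. This stands as a limit: the reading is inferred from walking being the secondary objective. The inference is strong, and the confounding of the resting pair does not depend on it.

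**The four readings together might rescue the design.** If the masked walk came third and the unmasked walk fourth, the order would be unmasked, masked, masked, unmasked. With columns for intercept, walking, mask and linear time, that design has rank 4 of 4, and the contrast (−1/2, +1/2, +1/2, −1/2) cancels a linear drift. This needs a walk order the Protocol does not state, a linear drift over equally spaced readings, no carryover, and the same mask effect at rest and after walking. If the unmasked walk came first, the rank is 3 of 4. If the mask effect may differ between rest and walking, even the favourable order has rank 4 of 5. The resting effect remains unidentified.

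**The magnitudes are assumed.** This stands. Nothing in the Protocol shows that a drift exists, and the test used for illustration is not the one named. The exact cancellation in the last scenario is built in.

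**An analysis plan could deal with it.** It could not. Order is set when the data are collected, and no resting reading in the current design separates mask from period.

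**Settling intervals have a cost.** The Protocol lists exposure to COVID-19 during unmasked measurement as a foreseeable risk, and intervals before unmasked readings could lengthen that time. This stands and belongs in the cost. Changing the order alone does not need the intervals.

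**Conclusion.** The concern holds. At rest the Protocol fixes one order for every volunteer, so the resting contrast estimates mask effect plus period effect. That follows from the stated order alone.

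The size and direction of any bias are unknown. Under the stated assumptions, the chance of a falsely significant difference at n = 200 would run from 14% (drift 0.25 mmHg, SD 4) to 94% (drift 0.5 mmHg, SD 2), against a nominal 5%. These are not the error rates of the chi-square test the Protocol names.

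The finding is limited to the resting pair. The walk order is not stated, so the same confounding is not shown there. The change should be made before data collection, because it cannot be made afterwards.

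**What to change.** Amend the Intervention section so that each volunteer is allocated 1:1 to mask-first or no-mask-first at rest, and bring the Background sequence into line. Randomised allocation is preferable; strict alternation also balances the order but is predictable to staff. Use the same fixed settling interval before each resting reading. Record the order, and analyse the paired readings with a period term in a paired or mixed model. A drift common to both orders then cancels, provided there is no differential carryover.

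State the order of the two walks as well. The same allocation can be used there, with a fixed rest interval between walks.

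The cost is an allocation list, one model term and, if the intervals are adopted, a few extra minutes per volunteer. Some of that time would be unmasked and should be kept short in view of the exposure risk the Protocol already names. The planned readings, staff and number of participants stay the same.

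### Neither the order of the two 100 m walks nor a recovery interval between them is fixed, so carry-over into the secondary walking contrast cannot be ruled out

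*Protocol*

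**What the plan says.** The Protocol's Intervention section lists a resting reading without a mask, then a resting reading with one ("The second measurement will also occur at rest, but while subjects are wearing a mask"), and then the walks: "Lastly, end tidal carbon dioxide will be measured after each participant walks 100 meters, both with and without a surgical mask". The Setting section adds: "They will walk 100 meters twice, for a total of 200 meters". Each volunteer therefore contributes one masked and one unmasked walk, compared within person.

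The walking comparison serves the second objective: "A secondary objective is to assess possible changes in end tidal carbon dioxide while walking moderate distances while wearing a mask". It is also named in the null hypothesis under Research Question/Hypothesis.

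The protocol does not state which walk comes first, whether the order varies between volunteers, how long a volunteer rests between walks, or whether ETCO2 must be back at its resting value before the second walk.

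Two statements about the design do not agree with this. The closing paragraph of the Background describes readings at rest without a mask, "while resting with a mask and then after walking 100 meters in the mask", and mentions no unmasked walk. The Intervention section says "subjects will have their end tidal carbon dioxide levels measured in three separate scenarios", although two resting and two walking readings make four.

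**The concern.** The walking part is a two-period within-person comparison. Such a comparison isolates the mask only if the two periods are otherwise alike, or if their differences are balanced across conditions. Here a volunteer could walk, be read, change mask status and walk again within a minute or so, and every volunteer could do so in the same order. The first reading would then follow about 100 m of walking and the second about 200 m with little rest.

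With a single order for everyone, mask status and position in the sequence are the same variable, and no later analysis can separate them. Depending on the order and on the sign of the residual effect, carry-over could imitate a mask effect or hide one. The second case matters because the investigators hope to show that a mask does not raise ETCO2.

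The interval and the order are study procedures. They belong in the protocol and are not details that an analysis plan would normally supply.

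**Working it through.** **Step 1. The protocol's own figure.** 2 walks x 100 m = 200 m, which is correct. No alpha, power, effect size or SD accompanies the participant limit ("The maximum number of participants for this study will be 200"), so there is no sample-size calculation to reproduce.

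**Step 2. Illustrative carry-over model.** All inputs here are assumptions, because the documents give none.
- Walking speed 1.3 m/s, so a walk lasts 100/1.3 = 77 s.
- First-order response and recovery with time constant tau. I use 90-180 s, and 30-60 s as a faster alternative.
- Full (steady-state) exercise response of ETCO2, taken as a rise of 1 to 5 mmHg.

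If walk 1 starts from rest, it ends at 1 - exp(-77/tau) of the full response. After a gap g, the residual is that value x exp(-g/tau), and a fraction exp(-77/tau) of the residual is still present at the end of walk 2. The excess of reading 2 over reading 1 is therefore

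excess = [1 - exp(-77/tau)] x exp(-g/tau) x exp(-77/tau).

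| tau | gap 60 s | gap 300 s |
|---|---|---|
| 30 s | 0.923 x 0.135 x 0.077 = 0.010 | below 0.001 |
| 60 s | 0.723 x 0.368 x 0.277 = 0.074 | 0.723 x 0.0067 x 0.277 = 0.001 |
| 90 s | 0.575 x 0.513 x 0.425 = 0.125 | 0.575 x 0.0357 x 0.425 = 0.009 |
| 180 s | 0.348 x 0.717 x 0.652 = 0.163 | 0.348 x 0.189 x 0.652 = 0.043 |

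For tau of 90-180 s and a full response of 1 to 5 mmHg, the excess is 0.13 to 0.81 mmHg at a 1 minute gap (0.125 x 1 to 0.163 x 5) and 0.01 to 0.21 mmHg at 5 minutes (0.009 x 1 to 0.043 x 5). With the faster time constants the 1 minute excess is only 1-7% of the full response.

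**Step 3. Role of order.** Let c be the excess and p the share of volunteers whose masked walk is second. The bias in the masked-minus-unmasked mean is p x c - (1 - p) x c = (2p - 1) x c. This is c at p = 1, 0.5c at p = 0.75 and 0 at p = 0.5. If the two kinds of walk leave different residuals, c_u after an unmasked and c_m after a masked first walk, balance leaves (c_u - c_m)/2. Balance therefore removes equal carry-over only, and recovery time is needed for the rest.

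**Step 4. What such a bias could do.** Take n = 200, an assumed SD of paired differences of 2 to 4 mmHg and a two-sided 5% paired test of means. This is an illustration; the protocol names chi-square testing. SE = SD/sqrt(200) = 0.14 to 0.28 mmHg. With no true mask effect and everyone in one order, the rejection rate is Phi(-1.96 + b/SE) + Phi(-1.96 - b/SE) for bias b:
- b = 0.1 mmHg: 6% to 11%
- b = 0.25 mmHg, just above the largest 5 minute value: 14% to 42%
- b = 0.5 mmHg: 42% to 94%

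The 5 minute interval thus makes the bias small, but in the least favourable corner of the assumptions not negligible. That is a reason to balance the order as well.

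**Step 5. Would subtracting a pre-walk reading repair it?** A residual s at the start of walk 2 raises its end value by s x exp(-77/tau), but subtracting the pre-walk reading removes all of s. At tau = 90 s the error moves from +0.425s to -0.575s, so it changes sign and grows. At tau = 180 s it moves from +0.652s to -0.348s, so it changes sign and shrinks. A change score is not a dependable correction in this model.

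**The case against.** The strongest reply is that the protocol does not schedule the walks back to back. The sentence in Setting gives a count and a total distance and says nothing about timing. A reader might infer that the walks are consecutive and that the second reading is in fact contaminated. The text does not support that: it neither joins the walks nor separates them.

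A gap of zero can also be excluded. ETCO2 and oxygen saturation are both to be read after the first walk, and the mask must be put on or taken off. The zero-gap value of the model, 23-24% of the full response, is therefore not a realistic case.

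The direction is open too. Residual CO2 load would raise ETCO2, while residual extra ventilation would lower it. The model assumes a rise only because some sign must be chosen. The exercise response and the recovery time are likewise assumed, and after a short walk by healthy adults the effect may be small. If staff happened to balance the order and carry-over were equal in both orders, it would cancel.

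Finally, a reader might extend the point to the primary resting comparison. The Intervention section places the walks after both resting readings, so that comparison is not affected if this sequence is followed.

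All of this stands, and it limits the claim. It does not remove the gap: the protocol permits a short interval in one fixed order and requires nothing that would reveal incomplete recovery. The first post-walk reading does fall between the walks, but it is not a resting reading and does not show whether the volunteer had recovered.

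**Conclusion.** The point holds as a gap in procedure, not as a demonstrated bias. The protocol sets up a masked-versus-unmasked walking comparison within person and fixes neither the order nor the recovery between walks. Carry-over in that secondary contrast therefore cannot be ruled out, and with a single order it could not be undone after data collection.

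The size is unknown. Under the assumed time constants of 90-180 s it is about 13-16% of the full exercise response at a 1 minute gap and about 1-4% at 5 minutes; with faster recovery it is less. The conversion to mmHg depends wholly on an assumed response and should be read as a range only. The point merits correction before enrolment because the remedy is cheap, not because harm has been shown.

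**What to change.** In Intervention and Setting:

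1. Require a fixed minimum seated recovery between the two walks, for example 5 minutes.
2. Record a resting ETCO2 value just before the second walk, as a check on recovery. A tolerance as wide as 2 mmHg would not serve as the release criterion, because it exceeds the 0.13 to 0.81 mmHg excess illustrated for a 1 minute gap.
3. Randomise or alternate whether the masked or the unmasked walk comes first, and record the order for each volunteer.
4. Compare the two post-walk values directly within person. Do not make change from the pre-walk value the main analysis, for the reason in step 5 of the working.
5. Reconcile the Background summary and the count of three scenarios with the two walks described in Intervention and Setting.

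The cost is about 5-10 minutes and one extra capnography reading per volunteer on equipment already in use. No additional staff or participants are needed.
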